Appendix III – ECOG Performance Status Criteria

ECOG Score	Performance Status	Karnofsky Equivalent
0	Asymptomatic	100
1	Symptomatic, fully ambulatory	80-90
2	Symptomatic, in bed < 50% of the day	60-70
3	Symptomatic, in bed > 50% of the day but not bedridden	40-50
4	Bedridden	20-30
5	Dead	

Appendix IV – International Prognostic Scoring System (IPSS) Category and IPSS-R⁴¹

INTERNATIONAL PROGNOSTIC SCORING SYSTEM (IPSS) FOR MDS

Prognostic Variable	Survival and AML Evolution				
	Score Value				
	0	0.5	1.0	1.5	2.0
Marrow Blasts (%) ¹	< 5	5 –10	—	11–20	21–30
Karyotype ²	Good	Intermediate	Poor		
Cytopenias ³	0/1	2/3			

Risk Category	Combined Score
LOW	0
INT-1	0.5–1.0
INT-2	1.5–2.0
HIGH	≥ 2.5

IPSS-R Cytogenetic risk groups*,**

Cytogenetic prognostic subgroups	Cytogenetic abnormalities
Very good	-Y, del(11q)
Good	Normal, del(5q), del(12p), del(20q), double including del(5q)
Intermediate	del(7q), +8, +19, i(17q), any other single or double independent clones
Poor	-7, inv(3)/t(3q)/del(3q), double including -7/del(7q), Complex: 3 abnormalities
Very poor	Complex: >3 abnormalities

IPSS-R Prognostic Score Values*

Prognostic variable	0	0.5	1	1.5	2	3	4
Cytogenetics	Very Good		Good		Intermediate	Poor	Very Poor
BM Blast %	≤2		>2-<5%		5-10%	>10%	
Hemoglobin	≥10		8-<10	<8			
Platelets	≥100	50-<100	<50				
ANC	≥0.8	<0.8					

IPSS-R Prognostic Risk Categories/Scores*

RISK CATEGORY	RISK SCORE
Very Low	≤1.5
Low	>1.5 - 3
Intermediate	>3 - 4.5
High	>4.5 - 6
Very High	>6

*Greenberg, Tuechler, Schanz et al, Revised International Prognostic Scoring System (IPSS-R) for Myelodysplastic Syndrome, Blood 120: 2454, 2012.

**Schanz J et al, J Clin Oncology 2012; 30:820

Source: <http://ipss-r.com/> (accessed September 5, 2014)

Appendix V – WHO Based Prognostic Scoring System⁴²

Table 2. WHO Classification–Based Prognostic Scoring System for MDS

Variable	0	1	2	3
WHO category	RA, RARS, 5q-	RCMD, RCMD-RS	RAEB-1	RAEB-2
Karyotype*	Good	Intermediate	Poor	—
Transfusion requirement†	No	Regular	—	—

NOTE. Risk groups were as follows: very low (score = 0), low (score = 1), intermediate (score = 2), high (score = 3 to 4), and very high (score = 5 to 6).
 Abbreviations: MDS, myelodysplastic syndrome; RA, refractory anemia; RARS, refractory anemia with ringed sideroblasts; 5q-, myelodysplastic syndrome with isolated del(5q) and marrow blasts less than 5%; RCMD, refractory cytopenia with multilineage dysplasia; RCMD-RS, refractory cytopenia with multilineage dysplasia and ringed sideroblasts; RAEB-1, refractory anemia with excess of blasts-1; RAEB-2, refractory anemia with excess of blasts-2.
 *Karyotype was as follows: good: normal, -Y, del(5q), del(20q); poor: complex (≥ three abnormalities), chromosome 7 anomalies; and intermediate: other abnormalities.
 †RBC transfusion dependency was defined as having at least one RBC transfusion every 8 weeks over a period of 4 months.

Appendix VI – MDS Response Criteria

Based on International Working Group 2006 Modified Criteria

- Complete Remission (CR): $< 5\%$ myeloblasts with normal maturation of all cell lines
 - Persistent dysplasia will be noted
 - Peripheral Blood:
 - Hgb $\geq 11\text{g/dl}$
 - Platelets $\geq 100 \times 10^9/\text{L}$
 - Neutrophils ≥ 1000
 - Blasts = 0%
- Partial Remission (PR): all CR criteria if abnormal before except:
 - BM blasts decreased by $\geq 50\%$ over pre-treatment but still $>5\%$
- Marrow CR: Bone marrow with $\leq 5\%$ myeloblasts and decrease by $\geq 50\%$ over pretreatment with incomplete peripheral blood count normalization
- Hematologic Improvement (HI):
 - Hgb: Increase by $\geq 1.5\text{g/dl}$ or decreased PRBC transfusions by at least 4/8 week period (only PRBC given for Hgb $<9.0\text{g/dl}$)
 - Platelet Response: Absolute increase of $\geq 30 \times 10^9/\text{L}$ for those starting at $>20 \times 10^9/\text{L}$ For those $< 20 \times 10^9/\text{L}$ at baseline increase by 100% .
 - Neutrophil Response: at least 100% increase and an absolute increase of $>0.5 \times 10^9/\text{L}$
- Stable Disease: Failure to achieve at least a PR but no evidence of disease progression for >8 weeks
- Failure: Death during treatment or disease progression characterized by worsening cytopenias, increase percentage of marrow blasts, or progression to a more advanced MDS FAB subtype
- Cytogenetic Response:
 - Complete: Disappearance of any pre-treatment chromosomal abnormalities without the appearance of new ones
 - Partial: At least 50% reduction of chromosomal abnormality
- Disease Progression: Compared to pre-treatment values
 - Less than 5% blasts: greater than 50% increase to $>5\%$ blasts
 - $5\text{-}10\%$ blasts: greater than 50% increase to $>10\%$ blasts
 - $10\text{-}20\%$ blasts: greater than 50% increase to $>20\%$ blasts

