9.0 Study Endpoints

This study is designed as a two stage study of the combination of Decitabine and Vorinostat and haploidentical NK cell infusion. The primary endpoint is clinical response (CR + PR + HI) at the end of the required 2 cycles of therapy. An assessment of response differences between untreated/minimally treated and those with prior treatment failures will be conducted.

The secondary endpoints include evaluation of safety tolerability, the proportion of patients who become transfusion independent, the association of the in vivo NK cell expansion with clinical response, and 1 year Overall Survival.

Clinical responses are defined in Appendix VI.

Determination of toxicities will be important for this new combination. As per NCI CTCAE Version 4.0, the term toxicity is defined as adverse events that are classified as either possibly, probably, or definitely related to study treatment. The maximum grade for each type of toxicity will be recorded for each patient, and frequency tables will be reviewed to determine toxicity patterns. In addition, we will review all adverse event data that is graded as 3, 4, or 5 and classified as either “unrelated or unlikely to be related” to study treatment in the event of an actual relationship developing.

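### Appendix VI gives no response category to a marrow of exactly 5% blasts with recovered blood counts, so this patient is a non-responder in the primary endpoint unless hematologic improvement (HI) is met separately

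*Combined protocol and SAP*

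**What the plan says.** Section 9.0 states: "The primary endpoint is clinical response (CR + PR + HI) at the end of the required 2 cycles of therapy". It refers to Appendix VI for the definitions. Marrow CR and stable disease are not part of that sum.

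Appendix VI then sets the lines:

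- **CR:** "Complete Remission (CR): $< 5\%$ myeloblasts with normal maturation of all cell lines", with hemoglobin at least 11 g/dL, platelets at least 100, neutrophils at least 1000 and no peripheral blasts.
- **PR:** "Partial Remission (PR): all CR criteria if abnormal before except" for the marrow item, which reads "BM blasts decreased by $\geq 50\%$ over pre-treatment but still $>5" percent.
- **Marrow CR:** blasts of 5% or less, but only "with incomplete peripheral blood count normalization".
- **Stable disease:** "Failure to achieve at least a PR but no evidence of disease progression for >8 weeks".
- **HI:** hemoglobin up by at least 1.5 g/dL or a set reduction in red-cell transfusions; platelets up by at least 30 (doubling if below 20 at baseline); or neutrophils at least doubled with a rise above 0.5.

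Section 13.1 stops the trial if 5 or fewer of the first 15 patients respond. It calls the treatment unworthy of further study if 18 or fewer of 46 respond.

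**The concern.** CR stops just below 5% and PR starts just above it. The only line that includes 5% itself is marrow CR, which excludes patients whose counts have recovered and does not count toward the endpoint anyway. A near-complete responder can therefore score worse than patients on either side of the boundary.

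The gap lies inside the endpoint that drives both Simon decisions. If such a patient appears, the team must either record a non-response that the neighboring rules contradict, or settle the case ad hoc once the result is known. In a single-arm trial with a one-patient margin at stage 1, the second course is open to challenge.

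**Working it through.** **The plan's own figures.** From section 13.1: n1 = 15 (stop at 5 or fewer), n = 46 (fail at 18 or fewer), null rate 0.30, alternative 0.50. The chance of declaring success is the sum over x = 6 to 15 of P(X1 = x) × P(X2 ≥ 19 − x), with X1 ~ Bin(15, p) and X2 ~ Bin(31, p). It is 0.0499 at p = 0.30 and 0.803 at p = 0.50. The stated 5% and 80% reproduce, so the design figures are not in dispute.

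**Applying Appendix VI as printed.** Take an illustrative patient with baseline blasts 12%, hemoglobin 10.0, platelets 80 and ANC 0.8. After treatment hemoglobin is 11.2, platelets 105, ANC 1.3, with no peripheral blasts, normal maturation and no qualifying transfusion reduction. All CR blood values are met. HI is not: hemoglobin +1.2 (needs 1.5), platelets +25 (needs 30), ANC +62.5% (needs 100%).

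| Marrow after treatment | Fall from 12% | Category | Counts as response? |
|---|---|---|---|
| 4% | 67% | CR | yes |
| 5% | 58% | none of CR, PR, marrow CR, HI | no |
| 6% | 50% | PR | yes |

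The same 5% marrow with incomplete counts would be marrow CR. With better blood it has no response category.

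**Can such a patient enroll?** Yes, if treatment is required. In Appendix IV, marrow blasts of 11–20% score 1.5, which alone reaches INT-2 (1.5–2.0) and satisfies section 4.1.1. Severe cytopenia is not needed.

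**How narrow is the group?** Full recovery often brings HI with it:

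- Hemoglobin reaching 11 from 9.5 or below is a rise of at least 1.5.
- Platelets reaching 100 from 70 or below is, in general, a rise of at least 30 or a doubling.
- Neutrophils reaching 1.0 from below 0.5 more than double and rise by more than 0.5.

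With baseline hemoglobin 8, platelets 40 and ANC 0.5 and the same post-treatment values, all three HI rules are met and the patient counts. A lost patient therefore needs, roughly, baseline hemoglobin above 9.5, platelets above 70, no neutrophil or transfusion HI, and a reading of exactly 5%.

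**Role of baseline blasts.** PR needs blasts above 5% after a fall of at least half, so it is open only to baselines above 10%. The inversion (5% scored worse than a higher value) arises only there. At 10% or below, for example 8% to 5% (a fall of 37.5%), the printed text is simply a strict CR cut-off.

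**Stage 1.** With 6 responders in 15 the trial continues, and with 5 it stops. Reclassifying one patient is enough to change the decision.

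**The case against.** The strongest reply is that everything turns on one symbol in text read from a PDF. The ANC criterion is printed as at most 0.8 in the synopsis and section 4.1.7 but as below 0.8 in the Appendix I checklist, so symbols in this document do vary. That stands as a reason to check the original first. It does not remove the point, because Appendix VI as supplied prints the three signs distinctly and no other section assigns this case.

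A second reply is that the document elsewhere puts 5% in the higher band: IPSS and IPSS-R (5–10%) and the progression bands in Appendix VI. That supports assigning 5% to PR rather than CR. It does not support leaving it in neither.

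A reader might also infer a definite loss of power. If 1, 2 or 3 percentage points of true responders were lost, the 0.50 rate would become 0.49, 0.48 or 0.47, and power would fall from 80.3% to 77.3%, 73.9% or 70.2%. The documents do not support this. They give no frequency for the case, and a share of 0.1 points would leave power at 80.0%. Section 13.1 also sets 0.30 and 0.50 for the endpoint as Appendix VI defines it, and for that endpoint nothing is lost. On the same assumed shares, loosening the rule while 0.30 remains the null rate under the printed rule would raise type I error from 4.99% to 6.7%, 8.7% or 11.1%. Neither set of figures is a finding.

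Finally, any single classification can tip 6/15 to 5/15. That is true, but here the written rule itself produces the anomalous result.

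**Conclusion.** The gap is real as printed. Exactly 5% blasts with full count recovery is a non-response unless HI is met, while lower values, and higher values that meet PR, are responses. It is a small defect in the definition of the primary endpoint, not an error in the design figures. Its frequency is unknown and probably low given the HI rules. The one concrete consequence is that a single such patient could decide stage 1. The conclusion assumes that the symbols in the supplied text match the original and that the patient has normal marrow maturation. It deserves correction because a stated rule gives an inconsistent ordering and the repair is trivial.

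**What to change.** Check the CR symbol against the original PDF. If it is as printed, make the boundaries meet so that exactly 5% with recovered counts is a response. There are two ways:

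- **Write CR as 5% or less.** This is the simplest. It meets the PR line, uses the same cut-off as marrow CR, and does not overlap marrow CR, which requires incomplete counts. CR carries no 50%-fall test, so a patient going from 6% to 5% with recovered counts would also count, and the endpoint becomes slightly looser.
- **Write PR as 5% or more.** This keeps the 50%-fall test and closes the gap for baselines of at least 10%. Below that, 5% remains a non-response unless HI is met.

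Neither version assigns a category to recovered counts with abnormal maturation. If that case is meant to be covered, it needs its own sentence.

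Make the change by dated amendment to Appendix VI and the response form. For any patient already assessed whose category changes, report the result under both rules rather than reclassifying silently. No new data are needed.

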7.8.4 Prolonged Marrow Suppression

Hematologic toxicity due to allogeneic NK cells may occur later, and therefore hematologic recovery will be assessed beyond the expected chemotherapy-induced nadir.

Pancytopenia will occur with this regimen and should be treated as follows:

Anemia and thrombocytopenia are expected in all patients, and they will receive standard supportive transfusion care according to transfusion committee guidelines or as modified based on clinical parameters. Prolonged anemia or thrombocytopenia are not unexpected and will not count towards toxicity.

Neutropenia is expected in the majority of patients, and they will receive supportive care with prophylactic antibiotics as noted below. G-CSF and granulocytes should be avoided unless clinically indicated in the setting of severe, uncontrolled infection. If the clinical situation warrants growth factor use, then any remaining IL-2 administration will be stopped.

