8.1 Patient

8.1.1 Standard of Care and Investigational Treatment

	Pre-Treatment (within 28 days of treatment start)*	During each treatment course					4-6 weeks after 2 nd treatment course	Follow-up at Day 90, 180, 270, 360	
		Day 1 ¹	Day 5	Day 15 or 17	During IL-2 administration (Day 17-22)	Day 24, 31, 38, 45			
EVALUATIONS									
Written consent	X								
Medical history	X								
Disease Characteristics	X								
Pathology review of outside dx	X								
Transfusion History	X						X		
Concomitant meds	X	X					X		
Physical exam	X	X	X ⁶	X ⁶	X ⁶	X ⁶	X		
Vital signs	X	X		X					
Weight	X	X		X	3 x a week during IL-2	X			
Height	X								
ECOG Performance Status	X	X					X		
Survival Status								X ⁷	
LABORATORY									
CBC w/ diff ²	X	X	X	X	daily during IL-2	X	X		
Na, K, Cl, CO ₂ , BUN, creatinine, uric acid, phos, LDH, Mg	X	X	X	X		X			
ALT/AST, bili, total protein, albumin, alk phos	X	X		X		X			
Chest X-ray	X								
INR/PTT	X								
Pregnancy test ³	X								
HLA typing (low resolution)*	X								
Recipient Viral Serology	X								
ECHO/MUGA*	X								
Bone Marrow Bx/Asp ⁴	X ⁴					X ⁵	X ⁴		
Investigational TREATMENT									
Decitabine IV		Day 1-5							
Vorinostat PO			Day 6-15						
NK cell infusion (research)				Day 17					
IL-2 tiw for 3 doses (research)					X (start Day 17)				

* CBC, dff, CMP, chemistries within 14 days of study treatment start, HLA typing may be done at any time

- 1- Course 1 Day 1 evaluations need not be repeated if pre-study evaluations were done within 14 days of 1st treatment
- 2- CBC with diff weekly throughout all treatment with increased frequency as clinically indicated
- 3- Women of childbearing potential only; serum or urine
- 4- Bone marrow aspirate and biopsy with standard flow cytometry, conventional cytogenetics, and MDS/AML FISH panel will be conducted at study initiation and at the completion of the 2nd cycle for standard disease assessment or at time of study withdrawal if early termination.
- 5- Prior to course 2 ONLY in patients who enrolled in this study as a prior treatment failure per section 4.2.2 or any patient who is discontinuing study treatment after 1 course
- 6- Clinical assessments will occur at a minimum of weekly up until the NK cell infusion on Day +17 after which clinical assessments will occur daily until the day after the final IL-2 administration.
- 7- By record review, patient contact, etc.

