13.0 Statistical Considerations

13.1 Simon's Two-Stage Design and Sample Size

This is a single clinic Simon's optimum two-stage phase II clinical trial designed to determine the objective response rate (CR+PR+HI) after two courses of Decitabine and Vorinostat with haploidentical NK cells in patients with high risk MDS. The null hypothesis of the study is $P_{R0} \leq 0.30$ and alternative hypothesis is $P_{R1} \geq 0.50$. Based on this design and the assumption that the majority of patients will complete both cycles of therapy, a maximum of 46 evaluable patients will be used which is sufficient to maintain an overall type I error 5% while providing 80% statistical power.

In the first stage 15 patients will be enrolled, the trial will be terminated if 5 or fewer respond. If 6 patients respond, then the trial goes on to the second stage, and 31 more patients will be studied. If the total number responding is less than or equal to 18, then this approach will be deemed unworthy of further study.

Considering a predicted dropout rate of 10% during the two courses of therapy, in order to have 15 or 46 patients evaluable for the response rate, we will need a maximum of 17 patients (if the study is stopped by 1st stage) or 51 patients (if the study proceeds to 2nd stage).

Only patients completing both course 1 and 2 of planned therapy will be evaluable for response. However, all the patients with complete or partial treatment will be included in the evaluation for toxicities.

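### Appendix VI lets a transfused or single count, or a platelet rise from 5 to 10, score as hematologic improvement, so the primary test's 5% type I error is not protected

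*Combined protocol and SAP*

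**What the plan says.** Section 9.0 sets the endpoint: "The primary endpoint is clinical response (CR + PR + HI) at the end of the required 2 cycles of therapy". It then makes the appendix operative: "Clinical responses are defined in Appendix VI".

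Under Appendix VI, any one of three lineages gives HI:

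- **Hemoglobin:** a rise of at least 1.5 g/dl, or "decreased PRBC transfusions by at least 4/8 week period", counting only units given for hemoglobin below 9.0 g/dl.
- **Platelets:** an absolute rise of at least 30 x 10^9/L when the baseline is above 20. For those below 20 "at baseline increase by" 100%.
- **Neutrophils:** a doubling together with an absolute rise above 0.5 x 10^9/L.

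On transfusion, Section 7.8.4 states: "Anemia and thrombocytopenia are expected in all patients, and they will receive standard supportive transfusion care". Section 4.1.7 admits patients who depend on platelet or red-cell transfusion. The calendar in Section 8.1.1 collects transfusion history before treatment and at the response visit.

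Section 7.0 describes one formal response assessment, 4 to 6 weeks after the second course. Section 13.1 tests a null response rate of 30% against 50% and calls 46 evaluable patients "sufficient to maintain an overall type I error 5% while providing 80% statistical power".

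**The concern.** The hemoglobin-rise branch and both platelet branches ask for a change between two values. They do not say that either value must be free of recent transfusion, or that the change must be seen more than once. The transfusion history is collected, but no rule uses it to discount a transfused count. A patient given red cells or platelets shortly before the response visit can meet HI on that value alone. A patient whose platelets go from 5 to 10 meets it while staying below the limb's own cut of 20.

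Each such patient counts fully as a responder. In a single-arm trial judged against a fixed 30%, no control group would show how much of the observed rate comes from supportive care or fluctuation. The same calls count toward the six responses in 15 that open stage 2.

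**Working it through.** **Inputs from Section 13.1.** Null rate 0.30; alternative 0.50. Stage 1: 15 patients, stop at 5 or fewer responses. Stage 2: 31 more, 46 in total, with success at 19 or more.

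**Input not in the documents (assumption).** f is the share of true non-responders scored HI because of a transfused or one-off count. The plan gives no value, so a range is shown.

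**Step 1: reproduce the plan's figures.** For response probability p,

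P(worthy | p) = sum over x = 6 to 15 of Bin(x; 15, p) × P(Y ≥ 19 − x), with Y ~ Bin(31, p).

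- p = 0.30: 0.0499, agreeing with the stated 5%.
- p = 0.50: 0.803, agreeing with the stated 80%.

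The null rate at which this probability reaches exactly 0.05 is 0.3001, so the design has no slack.

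**Step 2: add false HI calls.** With a true rate of 0.30, observed rate = 0.30 + 0.70 × f.

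| f (assumed) | Observed rate | P(pass stage 1) | P(declared worthy) |
|---|---|---|---|
| 0 | 0.300 | 0.278 | 0.050 |
| 1% | 0.307 | 0.299 | 0.061 |
| 5% | 0.335 | 0.387 | 0.125 |
| 10% | 0.370 | 0.501 | 0.248 |
| 15% | 0.405 | 0.612 | 0.407 |

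**Step 3: how this depends on the true rate.** With a true rate of 0.20, observed rate = 0.20 + 0.80 × f. P(declared worthy) is 0.05%, 0.5% and 2.6% at f = 0, 5% and 10%. The inflation matters when the true rate is near the null, which is where the 5% is meant to hold.

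**Step 4: how long a transfusion-free window can be.** The last IL-2 dose is on day 22. If the 4 to 6 weeks run from there, the visit falls on day 22 + 28 = 50 to day 22 + 42 = 64 of course 2. A window of 8 weeks (56 days) would start between day −6 and day 8, so it would cover the period of expected marrow suppression. A patient with fewer than 4 baseline units per 8 weeks and one transfusion in that period would have no erythroid route. The rise branch would be barred, and a reduction of 4 units would be impossible. If 5% or 10% of true responders were lost this way (assumed), a true 50% would be observed as 0.50 × 0.95 = 0.475 or 0.50 × 0.90 = 0.45. Power would fall from 0.803 to 0.721 or 0.619. A short window is therefore needed.

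**Step 5: is a second count available?** The calendar note provides "CBC with diff weekly throughout all treatment with increased frequency as clinically indicated". The last listed course visit is day 45, and one CBC is listed at the response visit. On the timing in Step 4 these are 50 − 45 = 5 to 64 − 45 = 19 days apart. A second count at least a week away exists for some patients but is not assured for all.

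**The case against.** **The 5% claim may be correct as it stands.** A reader might infer that the 5% type I error is lost. The documents do not support that. The rule has alpha 0.0499 at a 30% response rate, and inflation needs two things they do not supply: a value of f above zero, and a 30% null that refers to genuine response. If the 30% was set for HI exactly as Appendix VI words it, this route does not inflate alpha. That stands. However, Section 13.1 gives no source or HI definition for the 30%, so the protection cannot be shown either.

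**Safeguards exist.** The red-cell reduction branch has an 8-week period and a hemoglobin condition. The neutrophil limb needs a doubling and an absolute rise, and Section 7.8.4 restricts G-CSF. This also stands, and it confines the point to the hemoglobin-rise and platelet limbs.

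**Section 7.8.4 does not say that patients are transfused at the response visit.** True. Transfusion-dependent patients may also have transfused baselines, which would shrink an apparent rise. This makes f uncertain in size, and it is why the scoring rule should cover both time points.

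**Appendix VI says it is based on the International Working Group 2006 criteria, so conditions might be carried over from there.** The appendix prints its own thresholds, Section 9.0 makes the appendix the definition, and the reference list has no entry for response criteria. Scorers could differ on what is implied.

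**Conclusion.** The point holds in this form. As written, a single transfused hemoglobin or platelet value, or a platelet doubling that stays below 20, is a primary-endpoint response. A baseline of exactly 20 has no rule. The type I error is therefore unprotected, which is a weaker statement than lost. P(declared worthy) is 6.1%, 12.5% or 24.8% for f = 1%, 5% or 10%, on three assumptions: a true rate of 30%, a null that means genuine response, and values of f chosen for illustration. The definitional gap itself needs none of these. It should be corrected because the endpoint decides both stages and the remedy is small.

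**What to change.** Change Appendix VI and Section 13. These are rules for scoring counts only and leave transfusion and G-CSF practice as it is.

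1. For baseline platelets of 20 x 10^9/L or below, require the doubled count also to end above 20. This also closes the gap at exactly 20.
2. Score the hemoglobin-rise and platelet limbs, at baseline and at response, only on counts with no transfusion of that product in a short stated window beforehand. Seven days is an example for platelets. For red cells, choose a window that does not reach back into the course 2 nadir. Judge patients still receiving red cells on the existing reduction branch.
3. Where a second CBC at least 1 week apart is available, require HI to hold on both, or report confirmed HI as a sensitivity analysis.
4. State in Section 13 that the 30% null refers to this HI definition.

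The windows also depend on the visit date. The Synopsis design text counts 4 to 6 weeks from the start of the second course, while Sections 3.0 and 7.0 count from the second course itself. These passages must be reconciled.

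Cost: appendix wording, possibly one extra CBC near the response visit, and a slightly lower observed response rate. Appendix VI has no platelet-transfusion reduction branch, so a patient with no platelet count outside the window could not score platelet HI. The sample size and the decision boundaries do not change.

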4.0 Selection of Patients

Study entry is open to adults regardless of gender or ethnic background. While there will be every effort to seek out and include females and minority patients, the patient population is expected to be no different than that of other studies of high risk myelodysplastic syndromes at the University of Minnesota and the Mayo Clinic.

Inclusion Criteria:

- 4.1 Diagnosis of high risk MDS that meets one of the following disease classifications and is requiring treatment:
 - 4.1.1 International Prognostic Scoring System (IPSS) Category: INT-2 or High Risk (see Appendix IV)
 - 4.1.2 International Prognostic Scoring System- Revised (IPSS-R) Category: High or Very High (Score of 5 or above) (Appendix IV)
 - 4.1.3 WHO Classification: RAEB-1 or RAEB-2 (Appendix V)
 - 4.1.4 WHO Classification: CMML that is not highly proliferative; WBC < 15k
 - 4.1.5 High risk cytogenetic abnormality as defined by presence of Monosomy 7, complex karyotype, or monosomal karyotype
 - 4.1.6 Therapy related MDS
 - 4.1.7 Severe cytopenias: Neutropenia (ANC \leq 0.8), platelet or PRBC transfusion dependent
 - 4.1.8 WHO Based Prognostic Scoring System (WPSS): High or Very High Risk (Appendix V)
- 4.2 Prior Treatment:
 - 4.2.1 Untreated/Minimally Treated: maximum of 2 cycles of hypomethylating agents (azacitidine or decitabine) without evidence of treatment failure as defined by progression to more advanced MDS Who classification or AML.

- 4.2.2** Treatment Failure: Patients who have not responded to or whose disease has progressed on hypomethylating agents (azacitidine or decitabine), 7+3 type induction chemotherapy, or immunosuppressive therapy such as ATG+CSA.
- 4.2.3** Patients must not have received treatment for their MDS within 4 weeks of beginning this study.
- 4.3** Age \geq 18 years of age
- 4.4** ECOG Performance Status 0-2 (Appendix III)
- 4.5** Available related HLA-haploidentical NK cell donor by at least Class I serologic typing at the A&B locus
- 4.6** Have acceptable organ function as defined below within 14 days (28 days for cardiac) of enrollment:
 - Renal: Creatinine: \leq 2.0 mg/dL
 - Hepatic: SGOT/SGPT $<$ 5 x upper limit of institutional normal (ULN)
 - Pulmonary: oxygen saturation \geq 90% on room air
 - Cardiac: LVEF by ECHO or MUGA \geq 40%, no uncontrolled angina, severe uncontrolled ventricular arrhythmias, or electrocardiographic evidence of acute ischemia or active conduction system abnormalities. QTc $<$ 500 msec

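### Hematologic improvement in Appendix VI has no baseline-abnormality condition, so a rise in a lineage that was normal at entry can count toward the primary endpoint

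*Combined protocol and SAP*

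**What the plan says.** Section 9.0 states: "The primary endpoint is clinical response (CR + PR + HI) at the end of the required 2 cycles of therapy". It then adds: "Clinical responses are defined in Appendix VI". HI alone is therefore enough for a response, and Appendix VI is where HI is defined.

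Appendix VI is headed "Based on International Working Group 2006 Modified Criteria". Its HI rules are:

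- **Hemoglobin:** a rise of at least 1.5 g/dl, "or decreased PRBC transfusions by at least 4/8 week period". The only hemoglobin limit, below 9.0 g/dl, governs which transfusions are counted.
- **Platelets:** "Platelet Response: Absolute increase of" at least 30 × 10^9/L for patients starting above 20, and a 100% rise for those starting below 20. There is a floor at 20 and no ceiling.
- **Neutrophils:** at least a 100% "increase and an absolute increase of" more than 0.5 × 10^9/L, with no limit on the starting count.

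PR in the same appendix requires "all CR criteria if abnormal before except" for the blast criterion. CR supplies count levels: hemoglobin 11 g/dl, platelets 100 × 10^9/L, neutrophils 1000.

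Section 4.1 admits a patient who meets any one of eight classifications. Severe cytopenia is one of them. RAEB-1 or RAEB-2, high-risk karyotype, CMML with WBC below 15k and "Therapy related MDS" each suffice alone.

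**The concern.** HI is meant to record recovery of a failing lineage. As written, it records any sufficiently large rise, including one in a lineage that was never failing. Such a rise says little about the regimen, yet it carries the same weight as a CR in the count that decides whether stage 2 opens and whether the regimen is judged worth further study.

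The omission works in one direction only: it can turn a non-responder into a responder, never the reverse. The two-stage rule has no slack, because its exact type I error is already at the 5% limit.

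There is also a reproducibility problem. One assessor may follow the text of Appendix VI, while another takes the heading as an invitation to apply thresholds from the cited criteria. They could then score the same patient differently.

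**Working it through.** **1. The plan's own figures.** Inputs from Section 13.1: null rate 0.30, alternative 0.50; 15 patients in stage 1, continue with 6 or more responders; 46 in total, success with 19 or more.

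P(success | p) = Σ over x = 6..15 of P(Bin(15, p) = x) × P(Bin(31, p) ≥ 19 − x).

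At p = 0.30 this is 0.0499; at p = 0.50 it is 0.803. The stated 5% and 80% are reproduced, so the sample-size arithmetic is not in question.

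**2. Can patients with normal lineages enter?** From Appendix IV:

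- IPSS: marrow blasts of 11–20% score 1.5, which is INT-2 with good karyotype and no cytopenia.
- IPSS-R: very poor cytogenetics (4) plus 5–10% blasts (2) gives 6, which is High, with no points from hemoglobin, platelets or neutrophils.

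A patient who qualifies on neutropenia alone (4.1.7) may also have normal platelets.

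**3. What the rules score, taken literally.**

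- Platelets 200 to 230: start above 20, rise of 30, so HI is met. The change is 30/200 = 15%, and the starting value is twice the appendix's own CR level of 100.
- Neutrophils 4.0 to 8.0 × 10^9/L: +100% and +4.0, so HI is met.
- Neutrophils 4.0 to 6.0: +50%, so HI is not met. A rise must be at least a doubling.

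**4. Effect on the decisions.** Let f be the share of true non-responders scored HI through a lineage normal at entry. The documents give no value for f. With a true rate of 30%, the counted rate is 0.30 + 0.70f.

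| f (assumed) | Counted rate | P(at least 6/15) | P(success) |
|---|---|---|---|
| 0% | 0.300 | 27.8% | 5.0% |
| 1% | 0.307 | 29.9% | 6.1% |
| 2% | 0.314 | 32.1% | 7.4% |
| 5% | 0.335 | 38.7% | 12.5% |

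**5. How large might f be?** Take fluctuation in platelets only, with an assumed within-patient CV of 10–15%.

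- *One later count, no drift:* P(Z ≥ 30/(baseline × CV × √2)) gives 8–17% at baseline 150, 14–24% at 200 and 20–29% at 250.
- *Two later counts both at least 30 above the same baseline, independent errors:* 2–7%, 5–11% and 9–15%.
- *One later count after a mean fall of 10% or 20% from 200:* P(Z ≥ (30 + fall)/(CV × √(200² + later mean²))), where the fall is 20 or 40 and the later mean 180 or 160. This gives 3–11% and 0.3–3%.

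f is the share of non-responders with such a lineage multiplied by the chance that one of them converts. Both are assumptions:

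- 20–30% × 20% gives f = 4–6% and P(success) 10.6–14.6%.
- 10% × 10% gives f = 1% and 6.1%.
- 20–30% × 3% gives f = 0.6–0.9% and 5.6–6.0%.

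**The case against.** **The heading names established criteria.** The Synopsis and Sections 3.0 and 7.0 also say response is assessed by International Working Group criteria, so assessors may apply a baseline threshold in practice. That stands as a reason not to assume every such rise will be counted. It does not close the gap: the heading says the criteria are modified, Section 9.0 makes Appendix VI the definition, and no threshold is reproduced there. What is left is ambiguity in the primary endpoint.

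**The regimen suppresses counts.** Section 7.8.4 expects pancytopenia, with anemia and thrombocytopenia in all patients. That would lower the frequency, as the drift calculation shows. Sections 3.0 and 7.0 place the assessment 4–6 weeks after course 2, when counts may have recovered, so the effect is reduced by an unknown amount and not removed.

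**Part of this is a different issue.** Appendix VI also asks for no confirmatory count for HI. The single-count figures above include that effect; requiring two counts cuts them to about half or less. Only the remainder belongs to the missing baseline condition. The noise calculation also covers platelets alone; fluctuation reaches a doubling of neutrophils far less easily.

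**CMML.** A reader might infer that proliferating CMML would be scored as a response. The documents do not support that as a statement of fact: entry is limited to CMML that is not highly proliferative, with WBC below 15k, and nothing says a doubling of neutrophils in such a patient is progression. What they do show is that the doubling would score as HI, and that Appendix VI gives no order of precedence between HI and its progression and failure criteria.

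**Conclusion.** The point holds as a gap in the definition of the primary endpoint. HI carries no baseline condition, PR does, and eligibility admits patients with normal lineages. Taken literally, a rise in a normal lineage is a response; given the heading, it may be scored inconsistently. The direction is certain, since the gap can only add responders.

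The size is not known. For f between 1% and 5%, the chance of declaring success at a true 30% rate is about 6.1% to 12.5%, against 5.0% as designed. With expected myelosuppression or confirmed counts it could stay close to 5%. A reader might infer that the trial's false-positive rate is 10–15%. That needs 20–30% of non-responders to have such a lineage and 20% of them to convert, under a single-count, no-drift model; none of these inputs is in the documents.

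**What to change.** In Appendix VI and on the response form:

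1. Score HI in a lineage only if that lineage was abnormal before treatment, and state the level for each. The appendix's own CR levels are one consistent choice: hemoglobin below 11 g/dl, platelets below 100 × 10^9/L, neutrophils below 1000 (1.0 × 10^9/L, reading the appendix's unitless figure as per microliter).
2. Keep patients with no assessable lineage in the denominator; they can still respond by CR or PR.
3. State that a patient who meets the progression or failure criteria is not an HI responder.
4. Apply the same rule to any patient already assessed. The protocol is at revision 7, so there may be some; the documents do not say.

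The cost is a short amendment, re-scoring from blood counts the study calendar already collects, and a slightly lower observed response rate. The 46 evaluable patients, the 0.0499 type I error and the 0.803 power of the decision rule are unchanged.
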